**Table 16-2 Assessment Schedule (Year 2)**

Period	Treatment Period (Year 2) 												PSDD Visit	EoT Visit 	EoS 4-wk post-transition visit/call
	Month														
	13	14	15	16	17	18	19	20	21	22	23	24			
Visit Window (days)	±5	±5	±5	±5	±5	±5	±5	±5	±5	±5	±5	±5			
Physical Exam													S	S	
Vital signs						X					X	X	X		
12-lead ECG													X	X	
Urine Pregnancy - WOCBP only			S			S			S		S	S	S		
Hematology			X			X			X		X	X	X	X	
Chemistry						X						X			
PT/INR, aPTT			X			X			X		X	X	X	X	
PK  and Free FXI / Total FXI 			X			X			X		X	X	X	X	
Antidrug antibodies (ADA) 			X			X			X		X	X	X	X	
Factor XI Coagulation Activity 			X			X			X		X	X	X	X	
Exploratory biomarkers 												X		X	
EQ-5D-5L and ACTS PROs 						X						X			
Study drug s.c. administration 	X	X	X	X	X	X	X	X	X	X	X	X		X	
Study drug p.o. accountability 	X	X	X	X	X	X	X	X	X	X	X	X	X	X	
Injection site inspection 	X	X	X	X	X	X	X	X	X	X	X	X	X	X	
Concomitant medications						X						X	X	X	
AE assessment						X						X	X	X	

S = results are documented in source documents only; PSDD = permanent study drug discontinuation; EoT = end of treatment period; EoS = end of study

 Subsequent treatment years will follow the same assessment schedule as Year 2

 Only collected from patients assigned to abelacimab

 May be collected in a subset of patients

 Patients assigned to abelacimab only; Dose can be administered at in-clinic or in-home visits by medically qualified, un-blinded study staff or designees as locally permitted. If administered in-home, assessments for concomitant medications, AEs, and other changes in health status will be conducted by sites via telephone or video call as locally permitted

 Patients assigned to rivaroxaban only; Accountability can be assessed at in-clinic visit or via virtual (e.g. video call) visit as appropriate and locally permitted

 The EoT visit for the randomized treatment period will also serve as Day 1 for the optional extension period. Refer to Table 17-3 for the optional extension period assessments. If a patient elects not to enter the extension, they will have the EoS visit as described in the protocol.

**Table 16-3 Optional Extension Period Assessment Schedule**

**Glossary of Abbreviations**

Abbreviation	Term
ACTS	Anti-Clot Treatment Scale
ADA	Anti-Drug Activity
AE	Adverse Event
AF	Atrial Fibrillation
ALT	Alanine Aminotransferase
aPTT	Activated Partial Thromboplastin Time
AST	Aspartate Aminotransferase
ATC	Anatomical Therapeutic Chemical
BLQ	Below Limit of Quantification
CI	Confidence Interval
CrCl	Creatinine clearance
CRNM	Clinically Relevant Non-Major
CV	Coefficient of Variation
DBP	Diastolic Blood Pressure
ECG	Electrocardiogram
eCRF	Electronic Case Report/Record Form
EoS	End of Study
EoT	End of Treatment
FXI	Factor XI
GI	Gastrointestinal
HR	Hazard Ratio
INR	International Normalized Ratio
ISTH	International Society on Thrombosis and Haemostasis
ITT	Intent-to-Treat
LLN	Lower Limit of Normal
MCH	Mean Corpuscular Hemoglobin
MCHC	Mean Corpuscular Hemoglobin Concentration
MCV	Medical Dictionary for Regulatory Activities
MedDRA	Mean Corpuscular Volume
NC	Not Calculated
NSAID	Non-Steroidal Anti-Inflammatory Drug
PCI	Potentially Clinically Important
PD	Pharmacodynamic
PK	Pharmacokinetic
p.o.	By mouth; orally
PPS	Per-Protocol Set
PRO	Patient-Reported Outcome
PT	Preferred Term
QOL	Quality of Life
RBC	Red Blood Cell
RDW	Red Cell Distribution Width
SAE	Serious AE
SAP	Statistical Analysis Plan
SBP	Systolic Blood Pressure
s.c.	Subcutaneous
SD	Standard Deviation
SI	International System of Units

Abbreviation	Term
SOC	System Organ Class
SSC	Study Steering Committee
TAFI	Thrombin Activable Fibrinolysis Inhibitor
TFLs	Tables, Figures and Listings
TEAE	Treatment Emergent AEs
ULN	Upper Limit of Normal
VAS	Visual Analogue Scale
WBC	White Blood Cell
WHO DD	World Health Organization Drug Dictionary

## 1. Source Documents

The Statistical Analysis Plan (SAP) was written based on the following documentation:

## 2. Protocol Details

### 2.1. Overall Study Design

This is a Phase 2b, event-driven, randomized, active-controlled, blinded endpoint, parallel-group study to evaluate the effect of two blinded doses of abelacimab relative to open-label rivaroxaban on the rate of major or clinically relevant non-major (CRNM) bleeding events in patients with atrial fibrillation (AF) who are at moderate-to-high risk of ischemic stroke.

Randomization into treatment groups will be stratified by the use of concomitant antiplatelet use at baseline (yes/no) and renal function (creatinine clearance [CrCl]  $\leq$ 50 ml/min or CrCl  $>$ 50 ml/min).

Eligible patients will be randomized into one of the following treatment groups:

- Treatment group 1: abelacimab 90 mg subcutaneous (s.c.) monthly
- Treatment group 2: abelacimab 150 mg s.c. monthly
- Treatment group 3: rivaroxaban 20 mg orally (p.o.) once per day with the evening meal [Note: Patients with a CrCl  $\leq$ 50 ml/min by the Cockcroft-Gault equation will receive the 15 mg p.o. daily dose of rivaroxaban]

The study is comprised of up to 4 periods: 1) screening (up to 4 weeks), 2) study drug treatment period through the end of treatment period (EoT) visit, 3) an optional extension period beginning at the EoT visit for qualifying patients to receive open-label abelacimab treatment (OLE period) if the study is discontinued early, and 4) transition period to appropriate standard of care (SoC) antithrombotic therapy per the discretion of the investigator through the End of Study (EoS) visit.

When the prespecified number of adjudicated clinical endpoint events for the final analysis have been reached, or if the study is to be stopped for any other reason, sites will be notified by the Sponsor's Clinical Study Team to schedule each patient for their EoT visit. As part of the EoT visit, the Investigator will make arrangements to transition the patient to the extension treatment period, or to end the study by transitioning the patient to a standard-of-care anticoagulation therapy following the guidelines in Section 7.1 of the protocol.

[figure not shown]
A separate statistical analysis plan will be created for the analysis of data in the study extension treatment period.

Since this is an event-driven study, the duration of treatment for a given participant in the study will depend on the rate of accrual of major and CRNM bleeding events in the whole study. As a result, the time on study drug will vary from patient to patient, depending on when

the patient enrolls into the study in relation to when the EoT visit has occurred for each patient. Based on event rates in similar trials, the estimated duration of the study at the start of the trial was expected to be approximately 27 months, but this may take longer depending on the rate of patient recruitment and clinical endpoint event rates.

The study design is presented in [Figure 1](#) below.

**Figure 1. Overall Study Design**

## 2.2. Study Objectives

### 2.2.1. Primary Objective

- To evaluate the effect of abelacimab relative to rivaroxaban on the rate of major or CRNM bleeding events as defined by the ISTH criteria.

### 2.2.2. Secondary Objectives

- To evaluate the effect of abelacimab relative to rivaroxaban on the rate of major bleeding events as defined by ISTH criteria.
- To evaluate the effect of abelacimab relative to rivaroxaban on the rate of major or minor bleeding events

### 2.2.3. Exploratory Objectives

### 2.3. Sample Size and Power

The primary endpoint is the composite of major or CNRM bleeding. The study is event driven. At the start of trial it was assumed a HR of 0.60 for each dose of abelacimab compared with rivaroxaban, thereby, a total of at least 166 events would provide at least 80% power for each abelacimab arm vs. rivaroxaban with a 2-sided alpha of 0.05. Given an expected 15% per year event rate in the rivaroxaban arm, a 10% annual dropout rate (death, withdrawal of consent,

lost-to-follow-up), approximately 1,200 patients would provide the requisite number of events over an approximate total trial duration of 27 months.

## 2.4. Primary Endpoint

- Time to first event of composite of International Society on Thrombosis and Haemostasis (ISTH)-defined major bleeding or CRNM bleeding events

## 2.5. Secondary Endpoints

- Time to first event ISTH-defined major bleeding events
- Time to first event ISTH-defined major or minor bleeding events

## 2.6. Exploratory Endpoints

## 2.7. Safety Variables

Safety endpoints include:

- Proportion of missed doses of abelacimab compared to the proportion of missed doses of rivaroxaban
- Adverse Events (AE)
- Laboratory parameters
- Vital Signs
- Electrocardiogram (ECG)
- Injection site reactions

## 2.8. Pharmacokinetic/Pharmacodynamic and Other Variables

- Trough abelacimab plasma concentrations at indicated time points
- Activated partial thromboplastin time (aPTT), free factor XI (FXI), and total FXI at indicated time points
- Percentage of abelacimab-treated patients who develop anti-drug antibodies (ADAs)
- Assess the impact of ADA development to safety, efficacy, PK and PD responses
- Exploratory coagulation parameters which may include, but not limited to, [REDACTED]  
[REDACTED]
- Exploratory evaluation of the association between [REDACTED]  
[REDACTED]

### 3. Analysis Populations and Dates

#### 3.1. Analysis Dates

The analysis dates to be used are defined as:

- EoT date = Earliest of a) the last dose+60 days or b) the EoT visit or c) death date or d) withdraw consent date or e) EoS visit date
- EoS date = Earliest of a) EoS visit or b) death date or c) withdraw consent date or d) lost to follow-up date; if no EoS date available, then impute EoT visit date

In the event that there is an open-label extension period in which the patient enrolls, the following analysis dates to be used are defined as:

- EoT date = Earliest of a) the last dose+60 days or b) the EoT visit or c) death date
- EoS date = Earliest of a) the last dose+60 days or b) the EoT visit or c) death date
- EoE date = Earliest of a) the last dose+60 days or b) the EoE visit or c) death date
- EoS extension date = EoS visit; if no EOS visit date available, then impute EoE date

In accordance with ICH E3 and E9, the following analysis sets will be used for the analyses.

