#### 4.1.3. Variable Obtained from Each Patient Required to Address the Clinical Question

For each patient in the study, the variable to address the clinical question is time from randomization to first event of composite of ISTH-defined major bleeding or CRNM bleeding events. Patients still alive and on study without an event will be censored at the EoT date. Patients lost to follow-up or who otherwise discontinued follow-up in the study prematurely without experiencing any event will be censored at the EoT date, as defined in Section 3.1. For patients who die without experiencing a primary event before death, the time to event will be censored on the date of death.

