## 5. Data Handling

### 5.1. Time Points and Visit Windows

#### 5.1.1. General Definitions

All assessment days will be related to the first day of first dose of treatment.

Day 1 is defined as first dose of treatment. Relative days after Day 1 are calculated as (assessment date – Day 1 date) + 1. Relative days prior to Day 1 are calculated as (assessment date – Day 1 date). The day prior to Day 1 is Day -1. Day 0 is not defined.

The date of the first dose of treatment for each patient will be taken from the electronic case report/record form (eCRF) page. If the date in this eCRF page is missing, alternatively the date of randomization will be used.

The date of the last dose of treatment for each patient will be taken from the eCRF page. For subjects receiving abelacimab, the last dose is latest Date of injection from the Study Drug SC Administration eCRF page.

For subjects receiving rivaroxaban, the last dose will come from the following sources, depending on the patient status:

- For those who permanently discontinue treatment, the last dose will be the permanent discontinuation date.
- For those who died but did not permanently discontinue treatment before death, the last dose will be the death date.
- For all other subjects who completed the treatment per the EoT visit page, the last dose will be the EoT visit date.
- If the last dose date is still missing, the last dose will be the last date pills were returned from the Study Drug PO Accountability page.

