## 6.6. Primary Analysis

### 6.6.1. Primary Analysis

The primary endpoint variable is defined as time to first event of composite of ISTH-defined major bleeding or CRNM bleeding events occurring from randomization through EoT date. Patients alive and on-study without an event will be censored at the EoT date. Patients lost to follow-up or who otherwise discontinued study follow-up prematurely without experiencing any event will be censored at the EoT date, as defined in Section 3.1. Patients who did not experience any event before death will be censored at the earlier of the date of death and EoT date.

The primary analysis will compare each abelacimab regimen with rivaroxaban for the time from randomization to first occurrence of major or CRNM bleeding in the On-Treatment Analysis Set. For each treatment regimen, the event rates at 6-month intervals will be estimated with 95% confidence intervals (CIs). For each comparison, the time to first event will be tested using the stratified log-rank test and the treatment effect estimated using the Cox proportional hazards model including treatment and the following two stratification factors as covariates:

- Planned use of concomitant antiplatelet medication use (e.g. aspirin and/or P2Y12 inhibitor) for the duration of the trial
- CrCl (Cockcroft-Gault)  $\leq 50$  ml/min

The hazard ratios with 95% CIs and two-sided p-values will be reported for both doses of abelacimab vs. rivaroxaban. A significance level of  $\alpha=0.05$ , without adjustment for multiplicative testing, will be used.

An inverted Kaplan-Meier plot will be drawn and estimates of the event rate at 6-month intervals will be presented.

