### 2.1. Change in the EoT date and EoS date in the randomized phase of the study for patients enrolled in the extension in section 3.1 of the SAP

The analysis dates to be used are defined as:

- EoT date = Earliest of a) the last dose+60 days or b) the EoT visit **-1 day** or c) death date or d) withdraw consent date or e) EoS visit date
- EoS date = Earliest of a) EoS visit or b) death date or c) withdraw consent date or d) lost to follow-up date; if no EoS date available, then impute EoT visit date **-1 day**

**As per the protocol version 5.0, EoT visit and Extension Day 1 will occur on same day.** In the event that there is an open-label extension period in which the patient enrolls, the following analysis dates to be used are defined as:

- EoT date = **Earlier of a) the last dose+60 days or b) the EoT visit -1 day**
- EoS date = **the EoT visit -1 day**
- EoE date = Earliest of a) the last dose+60 days or b) the EoE visit or c) death date
- EoS extension date = EoS visit; if no EOS visit date available, then impute EoE date

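### The primary censoring date has no last-contact term, so a patient lost while on treatment is typically counted as bleed-free for up to 60 days beyond the last observation

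*SAP*

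**What the plan says.** SAP 3.1 gives the on-treatment cut-off as a minimum of five dates. The first four are "EoT date = Earliest of a) the last dose+60 days or b) the EoT visit or c) death date or d) withdraw consent date", and the list ends "or d) withdraw consent date or e) EoS visit date". The EoS date in the next bullet, used for the ITT sensitivity analysis, does carry a term for loss: "or d) lost to follow-up date; if no EoS date available, then impute EoT visit date".

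SAP 6.6.1 applies the first of these dates to the lost: "Patients lost to follow-up or who otherwise discontinued study follow-up prematurely without experiencing any event will be censored at the EoT date". SAP 4.1.3 says the same when it defines the estimand variable, and Table 1 does so for study discontinuation.

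The 60-day clock starts at the last dose, defined in SAP 5.1.1. For abelacimab, "the last dose is latest Date of injection from the Study Drug SC Administration eCRF page". For rivaroxaban it is the permanent discontinuation date where there is one, then the death date or the EoT visit date according to status, and last of all the date of the final pill return.

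The post-lock SAP addendum, section 2.1, reopened the EoT list. It moved the EoT visit term back by one day and kept the remaining terms: "or c) death date or d) withdraw consent date or e) EoS visit date".

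**The concern.** A patient who stops responding while on treatment normally has no EoT visit, EoS visit, death date or withdrawal date. Only the first term is then left, and it is anchored on the last dose, not on the last time anyone learned whether the patient had bled. If those two coincide, the following 60 days enter the primary analysis as event-free time at risk, although no bleed in that period could have been reported.

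This lowers the estimated bleeding rate in any arm with losses. It distorts the hazard ratio if loss differs between arms, which is possible because abelacimab and rivaroxaban are given open-label, one by monthly injection and the other as daily tablets. Because the last dose comes from different sources in the two treatments, the unobserved time could differ by arm even with equal loss. The secondary bleeding endpoints inherit the rule through SAP 4.2 and 6.6.3. None of the sensitivity analyses in SAP 6.6.2 limits follow-up to the last contact.

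**Working it through.** **The plan's own figure.** SAP 2.3 assumes a hazard ratio of 0.60, two-sided alpha 0.05 and at least 80% power; allocation is 1:1:1.
- Schoenfeld events per comparison: 4 × (1.960 + 0.842)² / (ln 0.60)² = 120.3, rounded up to 121.
- Share of all events in one abelacimab arm plus rivaroxaban: (1 + 0.6)/(1 + 0.6 + 0.6) = 0.727.
- Total: 121/0.727 = 166.4, against 166 stated.
- Power at 166 × 0.727 = 120.7 pairwise events: 80.1%.

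The figure reproduces. (The protocol's sample-size paragraph prints 0.69 where the synopsis and SAP have 0.60; only 0.60 yields 166. That is a separate matter.) The target is a count of events, so the handling of event-free time after last contact does not alter it.

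**Unobserved time per lost patient.**
- Last contact at the last injection or pill return: 60 days, or 60/365.25 = 0.1643 years.
- A call 30 days after the last dose, then lost: 30 days.
- Contact 60 or more days after the last dose: none.

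**Share of person-time.** The documents give only a 10% annual dropout for death, withdrawal and loss combined, so the annual loss rate L is an assumption. With the full 60 days for every lost patient, the added person-time is L × 0.1643, and a 15% annual rivaroxaban rate becomes 15/(1 + L × 0.1643):

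| Assumed L per year | Added person-time | Rivaroxaban rate |
|---|---|---|
| 1% | 0.16% | 14.98% |
| 2% | 0.33% | 14.95% |
| 5% | 0.82% | 14.88% |
| 10% (all planned dropout is loss) | 1.64% | 14.76% |

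**Hazard ratio.** With roughly constant hazards, the estimate is about 0.60 × (1 + L_riva × 0.1643)/(1 + L_abel × 0.1643).
- Equal loss: 0.600.
- 5% rivaroxaban, 1% abelacimab: 0.60 × 1.00821/1.00164 = 0.604, a shift of about 0.7%.
- 1% rivaroxaban, 5% abelacimab: 0.596.
- Extremes of 10% against 0% in either direction: 0.610 and 0.590.

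**Bleeds that could go unrecorded.** Per lost patient over 60 days:
- Rivaroxaban: 1 − exp(−0.15 × 0.1643) = 0.024.
- Abelacimab, at 15% × 0.60 = 9% per year: 1 − exp(−0.09 × 0.1643) = 0.015.
- Twenty lost patients in an arm: 20 × 0.1643 = 3.3 person-years, and 0.49 (rivaroxaban) or 0.29 (abelacimab) expected bleeds.
- If loss were linked to bleeding, at an assumed fivefold hazard on rivaroxaban: 1 − exp(−5 × 0.15 × 0.1643) = 0.12 per lost patient.

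**The case against.** The strongest reply is that the clock runs from the last dose and the protocol arranges contact after it. Protocol 6.5.1 has roughly monthly calls during interruptions. Section 6.6 has a discontinuation visit, an EoS visit about 30 days later and then calls about every 12 weeks. Section 7.2 adds abbreviated visits or telephone contact. A discontinued patient who attends the EoS visit is capped by the fifth term of the list. This stands: a reader might infer that every lost patient gains 60 unobserved days, and the documents do not support that. The full gap arises only when last contact and last dose coincide.

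For rivaroxaban, pill return is only the last fallback. With multi-month dispensing and remote visits (protocol 6.8.1), it can precede the last contact, so the rule might even censor too early. Conversely, a discontinuation date entered after the last contact could lengthen the gap. The documents do not say how that date is set for a lost patient.

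A reader might also infer from the contrast with the EoS list that the on-treatment window outruns the ITT window, or that the ITT analysis is the safer one. Protocol 7.4 points the other way: a patient cannot formally be called lost until the scheduled end-of-study visit would have occurred. A formal lost date would then usually fall later than last dose plus 60 days, so the EoS date may have the same weakness.

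Finally, the effect is too small to change any plausible conclusion under the planning figures. That also stands.

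**Conclusion.** The rule is slightly wrong as written. The primary censoring date can lie beyond the last observation for a patient lost on treatment, the SAP sends such patients to that date explicitly, and the addendum revised the list without correcting it.

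The size is minor: about 0.16% to 0.8% of person-time for assumed loss of 1% to 5% per year, and about a 0.7% shift in the hazard ratio for 5% against 1% between arms. Event target and power are unaffected. These figures assume the full 60 days for every lost patient, constant hazards and loss unrelated to bleeding. The first assumption overstates the effect where contact followed the last dose; the last understates it if patients who bleed are more likely to disappear. Nothing here supports a claim that the primary result is materially biased.

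**What to change.** State in SAP 3.1, 4.1.3 and 6.6.1, through the addendum, that a patient lost to follow-up without a primary event is censored at the earlier of the EoT date and the last contact at which bleeding status was known. Adjudicated bleeds up to the existing EoT date should still count. Placing last contact inside the EoT minimum itself would be unsafe, because it could discard a fatal or later-documented bleed that occurred after the last contact.

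The formal lost-to-follow-up date should not be used, for the reason in protocol 7.4.

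The addendum places database lock at 08Mar2024. Rather than rewrite the primary rule after lock, the sponsor can run this as a documented sensitivity analysis and report the number of lost patients by arm. If that number is very small, the count alone nearly settles the point.

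The cost is one clause, one derived date and one extra model run. The documents do not say whether the date of the last bleeding assessment is held as a variable. It may have to be derived from visit and call records, and that should be checked first.

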#### **6.5 Study treatment interruptions**

Study drug may be interrupted at the Investigator's discretion for medical or surgical reasons.

Reasons for temporary study drug interruption may include a planned invasive procedure or surgery for which one would typically stop oral anticoagulation (see [Section 6.5.2](#)); clinical indication for a prohibited medication (see [Section 6.7.1](#)); a bleeding AE (see [Section 8.2](#)); or any other medical condition where the Investigator judges that it is in the best interests of the patient to temporarily interrupt study drug.

Since patients with AF are at underlying risk of stroke and systemic embolism, the duration of any study drug interruption should be kept to the minimum possible unless there is a contraindication to anticoagulation. Patients who have interrupted study drug should be re-evaluated regularly by the Investigator to determine the risks and benefits of resuming study drug.

For patients assigned to rivaroxaban, the eCRF page for study drug interruption should be completed for any temporary study treatment interruptions of 2 or more consecutive days and include the date/time of the last dose, the reason for the temporary interruption (e.g., procedures), and other required details.

For patients assigned to abelacimab, the eCRF for study drug interruption is required for any missed study treatment >45 days from the previous dose and include the date/time of the last dose, the reason for the temporary interruption (e.g., procedures), and other required details.

There is no limit on either the number of study drug temporary interruptions or the maximum length of a study drug temporary interruption. As long as the study has not completed, a patient who has interrupted study drug can resume study drug as soon as it is determined to be appropriate by the Investigator.

A patient who continues to be on study treatment interruption when the randomized period of the study has completed will be considered to have permanently discontinued study drug, will not be eligible for the extension and should complete a PSDD visit and a EoS visit approximately 30 days later (see [Section 6.6](#)).

Investigators are strongly encouraged to call the [REDACTED]

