#### 6.6 Permanent study drug discontinuation

Permanent study drug discontinuation (PSDD) is allowed at the Investigator's discretion or patient's request at any time. The Investigator should call the [REDACTED] in case of potential PSDDs.

If a patient has what is expected to be a permanent discontinuation of study drug, the patient should complete PSDD visit procedures outlined in the Assessment Schedule ([Appendix 3](#)). At the PSDD visit, unless the patient has a contraindication to anticoagulation, Investigators should arrange patients to be transitioned to appropriate SoC anticoagulation therapy minimizing any gap in anticoagulation since patients with AF are at underlying risk of stroke and systemic embolism (see [Section 7.1](#)).

Patients who permanently discontinue study drug will have an EoS visit approximately 30 days after the PSDD visit and then will be contacted periodically, approximately every 12 weeks, by telephone for SAEs and endpoints (see [Section 7.2](#)) until the site has been notified by the SSC that the randomized period of the trial has ended at which point the patient's participation in the study can be considered completed. Sites should not enter the patient as "complete" in the eCRF until the study has been declared complete, unless the patient has withdrawn their consent to be followed by all possible methods (i.e., in person, remotely, via third party) and refuses to permit review of the medical records.

In certain situations, patients who have previously permanently discontinued study drug and had an PSDD Visit can be allowed to resume study drug. The Investigator should contact the [REDACTED] to determine whether or not a patient who completed a PSDD visit can resume

study drug.

Any patient who permanently discontinues study drug and also wishes to withdraw consent for participation in the study must complete the protocol-specific withdrawal of consent procedures (see [Section 7.3](#)). The Investigator should contact the [REDACTED] to discuss cases in which a patient wishes to withdraw before the decision is made and withdrawal procedures are begun. Withdrawal procedures can begin only after discussion and confirmation that the patient's desire to withdraw full consent.

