## 7.2 Discontinuation of study treatment

Discontinuation of study treatment for a patient occurs when study drug is permanently stopped earlier than the protocol planned duration. Study drug discontinuation can be initiated by either the patient or the Investigator.

Study treatment should be discontinued from further study treatment for any of the following:

- Patient request
- The investigator judges that continued study drug administration is not in the best interest of the patient
- Pregnancy ([Section 8.6](#))

If a patient has what is expected to be a permanent discontinuation of study drug, the patient should complete the PSDD Visit procedures (see [Section 6.6](#)).

After study treatment discontinuation, at a minimum, in abbreviated visits, the following data should be collected at clinic visits or via telephone/video-call visits:

- signs and symptoms suggestive of bleeding, stroke, or TIA
- new/concomitant treatments
- AEs/SAEs

If the patient cannot or is unwilling to attend any visit(s), the site staff should maintain regular telephone contact with the patient, or with a person pre-designated by the patient, approximately every 12 weeks.

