### **10.1 Analysis sets**

- On-Treatment: will consist of all randomized patients who received at least one dose of study drug. Patients will be considered to be on-treatment if within 60 days of their last dose of study drug up to the EoT visit of the randomized treatment period.
- Intent-to-Treat (ITT): all patients randomized and dosed to be analyzed according to randomized treatment assignment. Events occurring from randomization through EoS of the randomized treatment period will be included in the analysis.
- Per Protocol: All randomized patients with a treatment compliance rate of at least 80% and do not have any major protocol violations as defined in the final SAP.
- On-Treatment Extension: will consist of all patients who received at least one dose of abelacimab in the extension period. Patients will be considered to be on-treatment if within 60 days of their last dose of study drug to the EoE visit of the extension period.

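### As written, the SAP ends ITT follow-up of permanent discontinuers at an EoS visit about 30 days after the PSDD visit, so later endpoints enter neither analysis, and the same visit can shorten the primary 60-day window

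*SAP*

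**What the plan says.** **Follow-up of discontinuers.** Protocol section 6.6: "Patients who permanently discontinue study drug will have an EoS visit approximately 30 days after the PSDD visit and then will be contacted periodically". The calls come about every 12 weeks, ask for SAEs and endpoints, and go on until sites are told that the randomized period is over. Protocol section 7.2 lists "signs and symptoms suggestive of bleeding, stroke, or TIA" among the data to collect after stopping.

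**ITT window.** Protocol section 10.1: "Events occurring from randomization through EoS of the randomized treatment period will be included in the analysis". SAP section 6.6.2 counts ITT events, and censors, at the EoS date of SAP section 3.1: "EoS date = Earliest of a) EoS visit or b) death date or c) withdraw consent date or d) lost to follow-up date". Addendum section 2.1 keeps this wording for patients outside the extension. It changes only the fallback date if no EoS date exists.

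**Primary window.** Protocol section 10.1 treats a patient as on treatment for 60 days after the last dose, up to the EoT visit. SAP section 3.1 defines the EoT date as the earliest of five dates. Item a) is last dose plus 60 days and item e) is the EoS visit date. Addendum section 2.1 keeps item e) for patients outside the extension.

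**Last dose.** SAP section 5.1.1 takes the latest injection date for abelacimab. For a rivaroxaban patient who stops permanently it takes the permanent discontinuation date.

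**The concern.** For a permanent discontinuer, the visit that the protocol calls EoS comes before follow-up ends, yet the SAP uses a visit of that name to end follow-up. Endpoints that the trial goes on collecting would then be left out of the one analysis meant to hold them.

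Among the sensitivity analyses listed in SAP section 6.6.2, only the ITT one runs past the EoT date (section 6.6.4 is redacted). If it adds little or no time for discontinuers, its agreement with the On-Treatment result says little about whether stopping was related to bleeding risk.

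Item e) raises a second question. The protocol gives the primary analysis a 60-day window after last dose with no EoS-visit limit, and the SAP adds one.

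**Working it through.** The plan states no figure for this point, so there is none to reproduce. The check has two parts.

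**1. Dates.** Let D be the days from last dose to the PSDD visit, with no earlier death, withdrawal, loss or EoT visit.

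- EoS visit (ITT end) = D + 30
- EoT date (primary end) = min(60, D + 30)
- Time that ITT adds = max(0, D − 30)
- First 12-weekly call ≈ D + 30 + 84

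| D | ITT ends, day | Primary ends, day | ITT adds, days | First call, day |
|---|---|---|---|---|
| 0 | 30 | 30 | 0 | 114 |
| 30 | 60 | 60 | 0 | 144 |
| 45 | 75 | 60 | 15 | 159 |

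The two windows coincide for D up to 30. Below 30 the 60-day window is cut, to about 30 days at D = 0. Because last dose is dated differently by arm, D could differ by arm. For example, a rivaroxaban patient seen on the stopping date has D = 0, and an abelacimab patient seen a month after the last injection has D of about 30.

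For a PSDD visit at month 6, 12 or 18 of a 27-month period, the follow-up lost is about 27 − 6 − 1 = 20, 27 − 12 − 1 = 14 or 27 − 18 − 1 = 8 months.

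**2. Size.**

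From SAP section 2.3: λ = 0.15 first events per year (the rivaroxaban planning rate, used here for all arms) and a 27-month trial.

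Assumed:
- uniform accrual over 12 months, so follow-up T is uniform on 15 to 27 months
- death μ = 0.04 per year
- stopping s = 0.05, 0.10 or 0.15 per year, unrelated to bleeding risk
- event rate after stopping ρ = 0.05 to 0.15 per year
- D = 0 to 60 days
- no other loss to follow-up, and no transition period for completers

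With a = λ + μ + s, k = ρ + μ, c = (D + 30)/365.25 and G(k, x) = (1 − e^(−kx))/k, the person-years per patient, averaged over T, are:

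- on drug: G(a, T)
- after stopping: ∫₀ᵀ s e^(−at) G(k, T − t) dt
- dropped: ∫₀^(T−c) s e^(−at) e^(−kc) G(k, T − t − c) dt

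Share of person-time dropped = dropped/(on + after). Share of first events dropped = ρ·dropped/(λ·on + ρ·after).

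Example with s = 0.10, D = 30, ρ = 0.10: on = 1.3651, after = 0.1216, dropped = 0.1003.
- Person-time: 0.1003/1.4867 = 6.7%
- First events: 0.01003/(0.2048 + 0.0122) = 4.6%

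Ranges over D = 0 to 60 and ρ = 0.05 to 0.15:

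| Stopping per year | Stop event-free (s × on) | Person-time dropped | First events dropped |
|---|---|---|---|
| 5% | 7% | 3.0–4.0% | 1.1–3.7% |
| 10% | 14% | 5.9–7.7% | 2.2–7.2% |
| 15% | 20% | 8.6–11.2% | 3.3–10.5% |

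A later PSDD visit lowers these. At D = 180 a simulation of the same model gives 1.8–2.0% of person-time and 0.7–1.8% of events for 5% stopping, rising to 5.3–5.8% and 2.1–5.3% for 15%.

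**The case against.** **A study-end date was probably intended.** Protocol section 5 follows all randomized patients to the EoS visit even after stopping. Section 7.1 places that visit just before participation concludes. Section 6.6 tells sites not to enter a discontinuer as complete "in the eCRF until the study has been declared complete". SAP section 6.2 takes completion status from the End of Study form. Under that reading ITT keeps the later events. This stands as evidence of intent, but none of these passages defines the date in SAP section 3.1. The documents do not say which eCRF date supplies the EoS visit for a discontinuer, and the only such visit that protocol section 6.6 schedules for them is the one about 30 days after PSDD. For the same reason a reader should not infer that events were in fact discarded.

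**Other passages may seem to confirm a mid-trial EoS visit.** Protocol section 6.5 says certain patients "should complete a PSDD visit and a EoS visit approximately 30 days later", but it concerns those still interrupted when the randomized period has completed, so their visits fall at study end. The column "EoS 4-wk post-transition visit/call" in Table 16-2 fits either reading. The point rests on section 6.6.

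**Not everything learned at later calls is lost.** The cut-off acts on event date. A bleed dated on or before the EoS visit but reported later still counts, and SAP section 6.7.2 displays all bleeding information with no EoS limit stated there.

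**The effect may be small.** In one simulation (SAP section 2.3 inputs, equal rates after stopping in all arms, PSDD at day 30, 5 to 10% stopping per year) the HR is 0.604–0.609 under the literal rule and 0.609–0.633 with full follow-up. The shift is at most ln(0.633/0.604) ≈ 0.05. With 121 pairwise events the standard error of the log HR is about 2/√121 = 0.18, so this is about a quarter of one standard error. That is fair for lost time and dilution. The model has stopping unrelated to risk, so it does not address risk-related stopping. A major or CRNM bleed that itself led to stopping is already counted, so what remains is stopping for minor bleeds or other risk-related reasons.

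**Conclusion.** The point holds for the SAP as written and should be fixed. Events in permanent discontinuers dated after the EoS visit fall outside both analyses, contrary to protocol section 10.1. For these patients ITT adds nothing when the PSDD visit is within 30 days of last dose.

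The loss is about 3 to 11% of ITT person-time and 1 to 11% of first events. This rests on assumed stopping of 5 to 15% per year, PSDD visits 0 to 60 days after last dose, and stopping unrelated to bleeding risk. The documents give neither discontinuation rates nor PSDD timing, and the direction of any effect on the HR is unknown.

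A reader might infer that the primary analysis is untouched, or that it is biased toward one arm. Neither follows. Item e) can shorten the primary window, and the last-dose rules could make this differ by arm, but the documents do not show how often or in which direction.

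**What to change.** 1. For the ITT sensitivity analysis, follow permanent discontinuers to the last contact with known endpoint status, up to the declared end of the randomized period, death or consent withdrawal. Count all CEC-adjudicated events to that date. Keep the current dates for other patients, including the day before the EoT visit for those entering the extension.
2. State in SAP section 3.1 which eCRF date is the EoS visit for a discontinuer, and reconcile it with protocol sections 6.6 and 10.1.
3. Reconcile item e) of the EoT date with the 60-day window in protocol section 10.1.

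The cost is a short addendum and one run, since the protocol already has sites collect these endpoints. The database was locked on 08Mar2024, so the change must be labelled a post-lock correction or an added sensitivity run. The run includes standard-of-care time and so targets a different estimand. It may move the HR toward 1, and the report should say so.
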